5.7.1.1. Sensitivity of the Primary Efficacy Analysis

Robustness of the primary analysis statistical method will be assessed through sensitivity analyses, including an ITT analysis and an on-treatment analysis of the percent change in calculated LDL-C from baseline to week 24 using a mixed-effect model with repeated measures (MMRM) approach.

Sensitivity to Non-Good Clinical Practice (GCP) Compliant Sites

To assess the impact of non-GCP compliance sites on the primary efficacy endpoint, the primary efficacy analysis will be performed excluding non-GCP compliant sites. Sites known to be non-GCP compliant at the time of database lock will be identified for this analysis before database lock. Any additional sites determined to be non-GCP compliant post-database lock will be separately identified.

Sensitivity to the Handling of Missing Data

Sensitivity analyses will be conducted to assess the robustness of the primary efficacy analysis with regards to the handling of missing data ([Little RJ 2012](#)).

Mixed-effect Model with Repeated Measures (MMRM) Approach

The percent change from baseline in calculated LDL-C at week 24 will be analyzed in the ITT population using a mixed effect model with repeated measures (MMRM) approach. All post-baseline data available within week 1 to week 24 analysis windows regardless of adherence to treatment and subsequent therapies will be used and missing data are accounted for by the MMRM model. The MMRM model assumes “missing-at-random” (MAR). The model will include the fixed categorical effect of time point (weeks 1, 2, 4, 8, 12, 16, 20, and 24), as well as the continuous fixed covariates of baseline calculated LDL-C value.

This model will be run using Statistical Analysis Software (SAS) mixed procedure with an unstructured correlation matrix to model the within-patient errors. Parameters will be estimated using restricted maximum likelihood method with the Newton-Raphson algorithm. Denominator degrees of freedom will be estimated using Satterthwaite’s approximation. This model will provide baseline adjusted least-squares mean estimate at week 24 with their corresponding standard error.

Sensitivity to On-treatment Calculated LDL-C Values

To assess the robustness of the more clinically relevant data for the analysis of the primary efficacy endpoint, the same statistical analysis method approach as described above for the MMRM approach will be applied in the mITT population. The intent-to-treat estimand will be replaced by the on-treatment estimand.

The on-treatment estimand used for the primary efficacy sensitivity analysis is the “while on treatment strategy” estimand. The on-treatment estimand for the primary efficacy sensitivity analysis is defined as:

- A. The patient population is defined as the Modified Intent-to-treat (mITT) population (Section 3.1.2).
- B. Same definition as the treatment policy estimand described for primary efficacy analysis.
- C. The intercurrent events of interest are the administration of study treatment and the administration of subsequent therapies. The discontinuation of study treatment impacts the primary efficacy endpoint values used in the analysis, specifically including those values collected during the efficacy treatment period (Section 3.1.2). For subsequent therapies, any changes are ignored in the analysis.
- D. The population-level summary for the primary efficacy sensitivity analysis is the least square estimate of mean calculated using the mixed effect model with repeated measures (MMRM) approach.

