3.1.2. Modified Intent-to-Treat (mITT)

The modified ITT (mITT) population is defined as all patients who received at least 1 dose or part of a dose of open-label study drug in Part B and have an evaluable primary efficacy endpoint. The endpoint is considered as evaluable when both of the following conditions are met:

1. Availability of at least 1 measurement value for calculated LDL-C before first dose of study drug (i.e., baseline).
2. Availability of at least 1 calculated LDL-C value during the efficacy treatment period and within one of the analysis windows up to week 24. The efficacy treatment period is defined as the time from the first study drug administration up to 35 days after the last study drug administration in Part B.

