4.7.1. Primary Efficacy Variable (s)

The primary efficacy endpoint for Part B is:

- The percent change in calculated LDL-C from baseline to week 24 (intent-to-treat [ITT] estimand) in Part B. The primary endpoint is defined as: $100 \times (\text{calculated LDL C value at week 24} - \text{calculated LDL-C value at baseline}) / \text{calculated LDL-C value at baseline}$.

The baseline LDL-C value is defined as the last calculated LDL-C value obtained before the first dose of study treatment in Part B. The calculated LDL-C at week 24 will be the LDL-C value obtained within the week 24 analysis window.

The intent-to-treat estimand used for the primary efficacy analysis is the treatment policy strategy, specifically the occurrence of the intercurrent events is irrelevant; the value for the primary efficacy endpoint is used regardless of whether or not the intercurrent events occur. The intent-to-treat estimand for the primary efficacy analysis is defined as:

- A. The patient population is defined as the Intent-to-treat population (Section 3.1.1).
- B. The primary efficacy endpoint is defined above.
- C. The intercurrent events of interest are the administration of study treatment and the administration of subsequent therapies. The interruption of study treatment and the change in subsequent therapies are ignored, and the value for the primary efficacy endpoint is used regardless of adherence to study treatment and subsequent therapies.
- D. The population-level summary for the primary efficacy endpoint is evinacumab mean value, SE and 95% confidence interval.

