5.7.3. Summary of Results by Time Point

For Part B, central laboratory values (in conventional (US) and international units), percent change from baseline, and/or when appropriate absolute change from baseline (in conventional and international units) will be summarized at protocol scheduled visits by total patients for calculated LDL-C, Total-C, non-HDL-C, Apo B, and Lp(a). The time profile of each parameter will be plotted with the corresponding standard errors. Further details are described below:

- For lipids other than Lp(a): observed and imputed values, change from baseline (as applicable), and percent change from baseline, will be summarized using the same ITT estimand and PMM approach for missing data for all patients in the ITT population as described for endpoints above by mean and SE at all planned time points (see Section 5.7.2.1).
- For Lp(a): observed and imputed values, and percent change from baseline, will be summarized using the same ITT estimand and multiple imputation approach for missing data for all patients in the ITT population as described above by mean and SE at all planned time points (see Section 5.7.2.1).
- Observed data raw values, change from baseline (as applicable), and percent change from baseline response variables will be descriptively summarized using the ITT estimand for all patients in the ITT population by patient counts, mean, SD, median, Q1, Q3, minimum, and maximum at all planned time points.
- Observed data raw values, change from baseline (as applicable), and percent change from baseline response variables will be descriptively summarized using the on-treatment estimand for all patients in the mITT population by patient counts, mean, SD, median, Q1, Q3, minimum, and maximum at all planned time points. On-treatment estimand is defined as all secondary efficacy endpoints values collected during the efficacy treatment period (Section 3.1.2).

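### The on-treatment sensitivity analysis is labelled while-on-treatment, but as specified it estimates a hypothetical quantity: the week-24 change had all mITT children continued evinacumab

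*SAP*

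**What the plan says.** SAP section 5.7.1.1 sets out a sensitivity analysis restricted to on-treatment LDL-C values, introduced as the check on the data of greater clinical relevance. Its strategy is named outright: "The on-treatment estimand used for the primary efficacy sensitivity analysis is the “while on treatment strategy” estimand". The four attributes are then:

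- **Population:** mITT.
- **Variable (item B):** "Same definition as the treatment policy estimand described for primary efficacy analysis". That refers back to SAP section 4.7.1, where "The calculated LDL-C at week 24 will be the LDL-C value obtained within the week 24 analysis window".
- **Intercurrent events (item C):** after study drug stops, only values from the efficacy treatment period count. SAP section 3.1.2 runs that period from the first dose "up to 35 days after the last study drug administration in Part B". Changes in other therapies are ignored.
- **Summary (item D):** the least-squares mean from the MMRM. The method is the one given just before for the ITT population, which assumes missing at random, and of which the SAP says "This model will provide baseline adjusted least-squares mean estimate at week 24 with their corresponding standard error".

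SAP section 5.7.3 reuses the name for a descriptive table by visit: "On-treatment estimand is defined as all secondary efficacy endpoints values collected during the efficacy treatment period". Protocol section 11.4.3.1 speaks only of an on-treatment MMRM analysis, so the strategy label comes from the SAP alone.

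**The concern.** Under a while-on-treatment strategy, the variable is each child's response up to the point of stopping, for example the last or the average on-treatment value. Here the variable stays fixed at week 24 while the data after stopping are removed. A child who stops early may then have no value for the stated variable, and a missing-at-random model fills the gap by assuming the child would have gone on like similar children still being dosed. That answers a different question: what week 24 would have looked like had treatment continued.

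What is at stake is the claim the result can carry. SAP section 7.2 allows the week-24 analysis to go into a submission dossier. A reader who takes the label at its word would read a prediction under continued dosing as the response children had while on drug. Part B is small: at the current protocol's 14 children, each one carries 1/14, or about 7%, of the mean.

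**Working it through.** **1. Can an early stopper have an on-treatment week-24 value?**

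Inputs: Part B dose days 1, 29, 57, 85, 113 and 141 (protocol Table 2); efficacy treatment period ending at last dose + 35 days (SAP 3.1.2); week-24 efficacy window of days 155 to 196 (SAP 10.2, Table 3).

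| Last dose | Dose day | On-treatment period ends (dose day + 35) | Reaches day 155? |
|---|---|---|---|
| Week 0 | 1 | 36 | No |
| Week 4 | 29 | 64 | No |
| Week 8 | 57 | 92 | No |
| Week 12 | 85 | 120 | No |
| Week 16 | 113 | 148 | No |
| Week 20 | 141 | 176 | Yes |

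A usable value needs a last dose on or after day 155 − 35 = 120. A week-16 dose given at least 7 days late (113 + 7 = 120) just qualifies. Otherwise only children dosed at week 20 can have one.

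**2. What does the model then estimate?**

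The MMRM imputes no explicit value. Its likelihood predicts the missing week-24 response from the child's earlier on-treatment values and from the relation between visits seen in children still on drug. A large simulation shows the target. Its assumptions were 4,000 children and eight visits; mean change −30, −42 and −45 at weeks 1, 2 and 4, then −47; SD 18; correlation 0.7; and the 2 in 14 with the poorest week-4 values stopping, with data kept through week 8.

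| Quantity | Mean % change |
|---|---|
| True week 24 had all continued | −47.2 |
| Repeated-measures estimate, week 24 | −47.0 |
| While on treatment, last value | −47.1 |
| While on treatment, average of visits | −43.4 |

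The fit was a multivariate-normal likelihood by EM, using the known residual covariance in its update and no baseline covariate. It therefore illustrates the target and does not reproduce the SAP's REML model. The model recovers the had-all-continued mean. It agrees with the last-value summary only because the simulated effect is flat from week 8.

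**3. How large can the difference be?**

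The documents give no discontinuation rate, SD or visit correlation, so these are assumptions. Let m be the mean of children still on treatment, s the stoppers' mean last on-treatment change, ρ the visit correlation, k the number of stoppers and N the sample size. Then:

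- last-value mean = [(N − k)m + ks]/N
- model week-24 mean = [(N − k)m + k(m + ρ(s − m))]/N
- difference (model − last value) = −k(1 − ρ)(s − m)/N

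Take m = −47 (the adult and adolescent result in protocol section 1, borrowed here), N = 14, k = 2 and s = −10:

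- last value: (12 × −47 + 2 × −10)/14 = −584/14 = −41.7
- model, ρ = 0.5: predicted stopper −28.5; (−564 − 57)/14 = −44.4, difference −2.6
- model, ρ = 0.8: predicted stopper −17.4; (−564 − 34.8)/14 = −42.8, difference −1.1

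Over k = 1 to 3, s = −47 to −10, ρ = 0.5 or 0.8, and N = 14 (current protocol) or 18 (SAP, written to Amendment 1), the difference ranges in size from 0 to 4.0 points. The largest is k = 3, s = −10, ρ = 0.5, N = 14: 3 × 0.5 × 37/14 = 4.0. With k = 0 it is zero.

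**The case against.** The strongest reply is that the SAP hides nothing. It states the population, the data cut-off, the missing-data assumption and the week-24 least-squares mean, and its summary table in section 10.1 lists the analysis simply as an MMRM in mITT. No section says the result will be presented as what children experienced on drug. This is one supportive analysis in a trial without formal testing. The differences are also small beside the sampling error: with an assumed SD of 18 and 14 children, SE = 18/√14 = 4.8 and the 95% half-width is about 10.4 points. All of that stands and limits the weight of the point. It does not repair the label, because no section redefines the variable or calls the target hypothetical.

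Three stronger readings are tempting and are not supported:

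- *A reader might infer that the analysis flatters the drug.* That requires stoppers to have a lasting poorer response, which no document establishes. When stopping followed a poor week-4 value, the simulation gave −47.0 for the model against −47.1 for the last value. There is also no single while-on-treatment mean: in that simulation the last-value and average versions differ by 47.1 − 43.4 = 3.7 points.
- *A reader might infer that the section 5.7.3 table is a completers-only result.* It defines its own term, gives patient counts at each visit, and includes stoppers until their on-treatment period ends. Early stoppers are absent only from visits after that, week 24 among them. The fault there is the shared name.
- *A reader might infer that the main efficacy result is compromised.* The primary pattern-mixture analysis keeps treatment policy and imputes missing post-treatment values around the child's own baseline. Week-24 values collected after stopping, which protocol sections 8.4.2 and 9.1.2 ask sites to obtain, enter that analysis and the ITT MMRM.

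**Conclusion.** The point holds as a labelling error. For study-drug discontinuation, the mITT MMRM in SAP 5.7.1.1 targets a hypothetical strategy and does not estimate the while-on-treatment estimand it names. This follows from the SAP's own attributes and the day arithmetic on the nominal schedule, with the late week-16 dose as the one exception. The numerical consequence depends on the assumed number of stoppers, their last values and the visit correlation; the documents supply none of these. What changes is mainly what the result may be said to show.

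**What to change.** In SAP 5.7.1.1, replace the strategy label. State that the analysis uses a hypothetical strategy for study-drug discontinuation (week-24 percent change had all mITT patients continued evinacumab) and treatment policy for changes in other therapies. Report the result in those terms.

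In SAP 5.7.3, call the table a summary of observed on-treatment values at each visit, and do not give it the estimand's name.

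Only if the sponsor wants a while-on-treatment estimand, redefine item B as a response up to discontinuation, such as the last or the average on-treatment value, and give it a matching summary. The choice between these should be stated, since they can differ. Every mITT child has at least one on-treatment value by definition, so no new data are needed.

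The cost is a few lines of SAP text, plus one simple summary if the optional estimand is adopted. The SAP still reflects Amendment 1 and 18 Part B patients, so the change can go in when it is updated to the current protocol.

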5.7.1.2. Sub-group Analyses

To assess the homogeneity of the treatment effect across various subgroups, the percent change in LDL-C from baseline at Week 24 will be summarized by the following subgroups of interest, assuming there are enough patients in each subgroup level to perform the evaluation, using the same ITT estimand and PMM approach for missing data as for the primary endpoint:

- Gender (Female, Male)
- Age (≥ 5 to < 10 , ≥ 10 to < 12 years)

- Race
- Ethnicity
- The baseline apheresis status (Yes, No)
- Receptor-negative mutation in both LDLR or LDLRAP1 alleles (i.e. receptor-negative defined as a mutation resulting in termination codons, splice site mutations, frame shifts and large insertion/deletions) (Yes, No)
- LDLR activity (null/null [LDLR activity \leq 15%], not null/null [LDLR activity > 15%])

5.7.1.3. Multiplicity Considerations

Not applicable.

5.7.2. Analysis of Secondary Efficacy Variables for Part B

For the secondary efficacy endpoints (defined in Section 4.7.2), descriptive summaries and analyses will be performed in the ITT population, using values obtained regardless of adherence to study treatment and subsequent therapies (ITT estimand).

For descriptive summaries, percent change, and when appropriate change from baseline, in calculated LDL-C, total-C, non-HDL-C, Apo B, and Lp(a) will be provided at each time point during the 24-week treatment period. All measurements, scheduled or unscheduled, will be assigned to efficacy analysis windows defined in Appendix 10.2 in order to provide an assessment for these time points. Lipid assessments other than the ones provided by the central laboratory will be excluded. The time profile of each parameter will be plotted with the corresponding SEs.

Multiple types of measurements are planned to be analyzed during differing time points in the trial, specifically continuous measurements expected to have a normal distribution (e.g., percent change in calculated LDL-C), continuous measurements expected to have a non-normal distribution [e.g., Lp(a)], and binary measurements (e.g., proportion of patients with \geq 50% reduction in calculated LDL-C).

5.7.2.1. Continuous Endpoints Anticipated to have a Normal Distribution

Continuous secondary variables defined in Section 4.7.2 anticipated to have a normal distribution (i.e. lipids other than Lp(a)) will be analyzed using the same ITT estimand and PMM approach for missing data as described for the primary efficacy endpoint.

5.7.2.2. Continuous Endpoints Anticipated to have a Non-Normal Distribution

Continuous secondary efficacy variables defined in Section 4.7.2 anticipated to have a non-normal distribution (i.e. Lp(a)) will be analyzed using the multiple imputation approach for handling of missing values as described in Appendix 10.5, with data log-transformed before imputation process and then back transformed to create the imputed data sets using the TRANSFORM statement of SAS MI procedure.

The percent change from baseline at time point of interest will be derived from observed and imputed lipid values at this time point. Multiple imputation will be followed by robust regression model (Mehrotra, 2012), with the endpoint of interest as the response variable using M-estimation (using SAS ROBUSTREG procedure) with corresponding baseline value(s). Combined means estimates with their corresponding SEs and 95% CIs will be provided through the SAS MIANALYZE procedure.

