5.7.1. Analysis of Primary Efficacy Variable for Part B

While applying the ITT estimand, the percent change from baseline in calculated LDL-C at week 24 will be descriptively summarized for all patients in the ITT population using mean, SE, and 95% CI. Missing data will be imputed using a pattern mixture model (PMM) approach as described below (see Appendix 10.6 for more details).

In the PMM approach, different imputation strategies will be applied to calculated LDL-C values missing during the on-treatment period (i.e., within the time period from the first study treatment administration up to the day of last study treatment administration +35 days in Part B) versus calculated LDL-C values missing due to treatment discontinuation after the on-treatment period (i.e., after the day of last study treatment administration +35 days in Part B) based on the following assumptions:

- Patients within 35 days of their last study treatment administration in Part B would continue to show benefit from treatment similar to that observed at the scheduled time point. Therefore, calculated LDL-C values missing during the on-treatment period (e.g., samples obtained out-side the specified window for apheresis, no blood sample available although visit was performed, etc.) should be considered “Missing at Random” and imputed based on other observed measurements in the on-treatment period.
- Patients who stopped taking their study treatment in Part B no longer benefited from it after discontinuation, and thus tended to have calculated LDL-C values returning to baseline. Therefore, calculated LDL-C values missing after the on-treatment period should be imputed based on patient’s own baseline value.

Missing data from the ITT population will be imputed 100 times to generate 100 complete data sets, using the SAS MI procedure (using Markov Chain Monte Carlo). The 100 completed datasets of observed and imputed calculated LDL-C data will be used for the primary analysis.

For the percent change from baseline calculated LDL-C endpoint, the 100 complete datasets of observed and imputed calculated LDL-C data at week 24 will be analyzed using the SAS MEANS procedure. The SAS MIANALYZE procedure will be used to generate valid statistical inferences by combining results from the 100 analyses using Rubin’s formulae. Combined estimate for mean at Week 24 will be provided with the standard error (SE) and 95% confidence interval (CI). Formal statistical testing is not planned.

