5.7.2.3. Binary Endpoint Variables

Binary secondary efficacy endpoints defined in Section 4.7.2 will be descriptively summarized using the ITT estimand for all patients in the ITT population with the proportion and 95% CI. Missing data will be imputed using the same PMM approach as described for the primary efficacy endpoint.

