10.5. Detailed Description of the Multiple Imputation Procedure

The following is a detailed description of the multiple imputation procedure which will be used for analysis of the secondary efficacy endpoints.

In general, the missing pattern is anticipated to be not monotone, a two-step approach will be used:

- Step 1: the MCMC method will be used in conjunction with the IMPUTE=MONOTONE option to create an imputed data set with a monotone missing pattern. Set the SEED=17100 option in SAS MI procedure
- Step 2: Using the monotone data set from step 1, missing data will be imputed using the regression method. Set the SEED=34200 option in SAS MI procedure

The imputation model for step 1 will include the values of the analyzed parameter at baseline and planned time-points up to week 24.

The imputation model for step 2 will include the same variables as in step 1 with the following additional variables:

- age, BMI, and gender (age and BMI included as continuous variables).

Non-continuous variables included in the imputer's model (i.e., gender) are not expected to be missing.

In addition, for continuous efficacy variables anticipated to have a non-normal distribution (i.e. TG and Lp(a)), data will be log-transformed before imputation process and then back-transformed to create the imputed data sets using the TRANSFORM statement of SAS MI procedure.

For variables other than those continuous efficacy variables anticipated to have a non-normal distribution (i.e. TG and Lp(a)), for each simulation leading to negative imputed value, another value will be redrawn using MINIMUM option of SAS MI procedure.

The number of imputations (100) will be informally verified by replicating sets of 100 imputations and checking whether the combined results are stable. If not stable, the number of imputations will be increased and informally checked as above, and thus continued until stable estimates are obtained.

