Missing LDL-C values during the on-treatment period will be imputed from other on-treatment measurements assuming Missing At Random, using SAS® MI procedure.

Only LDL-C values collected during the on-treatment period will be included in the imputation model. This way, missing LDL-C values during the on-treatment period will be imputed based solely on observed on-treatment LDL-C values.

The imputation model will include baseline LDL-C value, and all LDL-C values at pre-specified visits. Since the pattern of missing data will necessarily be non-monotone, a Monte-Carlo

Markov Chain (MCMC) method will be used. A minimum value of 0 will be specified in order to avoid negative imputed LDL-C values.

A sample SAS code is provided below:

```
proc mi data=DATAIN out=DATAOUT nimpute=100 minimum=. 0 0 0 0 0 0 0 0 0 0  
SEED=17100;  
var LDL_BASE LDL_W1 LDL_W2 LDL_W4 LDL_W8 LDL_W12 LDL_W16 LDL_W20  
LDL_W24;  
run;
```

As stated above, the input dataset DATAIN will include only LDL-C values collected during the on-treatment period. Any LDL-C values collected during the post-treatment period will be excluded from the input dataset. In practice, the MI procedure will generate imputed values for all missing values (whether on-treatment or post-treatment), but only imputed values during the on-treatment period will be kept in the final datasets that will be analyzed. Imputed values during the post-treatment period will be discarded and replaced by imputed values described in the next paragraph.

Imputation of missing data after treatment discontinuation

Missing LDL-C values during the post-treatment period will be imputed assuming LDL-C values would on average return to baseline values.

For each patient, missing post-treatment LDL-C values will be imputed 100 times, using a random draw from a normal distribution (SEED=34200), with mean equal to patient's own baseline value and variance equal to the conditional variance at the specific time-point, given the baseline value.

Let Y_0 and Y_1 denote the LDL-C at baseline and at the specific time-point respectively. Since Y_0 and Y_1 are assumed to have a bivariate normal distribution, the conditional variance of Y_1 given Y_0 is:

$$Var(Y_1|Y_0 = y_0) = \sigma_1^2(1 - \rho^2)$$

Where σ_1^2 denotes the variance of Y_1 and ρ the coefficient of correlation between Y_0 and Y_1 .

The conditional variance will be estimated from observed data at the specific time-point.

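### Lp(a) missing after treatment discontinuation is imputed under MAR, without the return-to-baseline step applied to every other efficacy lipid, and no reason is given

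*SAP*

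**What the plan says.** All secondary efficacy endpoints in Part B carry the ITT estimand (SAP 4.7.2 and 5.7.2): an observed value counts whether or not the child is still on drug. The rules differ only for values that are absent.

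- **Premise (SAP 5.7.1).** "Patients who stopped taking their study treatment in Part B no longer benefited from it after discontinuation". The on-treatment period ends 35 days after the last dose.
- **Consequence (SAP 10.6).** "Missing LDL-C values during the post-treatment period will be imputed assuming LDL-C values would on average return to baseline values". The model that fills on-treatment gaps is fitted to on-treatment values only.
- **Other continuous lipids (SAP 5.7.2.1).** These "will be analyzed using the same ITT estimand and PMM approach for missing data as described for the primary efficacy endpoint".
- **Responder endpoint (SAP 5.7.2.3).** "Missing data will be imputed using the same PMM approach as described for the primary efficacy endpoint".
- **Lp(a) (SAP 5.7.2.2).** This "will be analyzed using the multiple imputation approach for handling of missing values as described in" Appendix 10.5, with a log transform, followed by robust regression.
- **Appendix 10.5.** "The imputation model for step 1 will include the values of the analyzed parameter at baseline and planned time-points up to week 24". The second step adds only "age, BMI, and gender (age and BMI included as continuous variables"). Neither step contains treatment status, and neither is limited to on-treatment values.

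SAP 5.7.3 repeats the split for the by-visit summaries, but for Lp(a) it cross-refers to 5.7.2.1, which is the PMM section. Protocol 11.4.3.2 had already set Lp(a) apart and left the imputation details to the SAP, so the two documents do not conflict on this point.

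**The concern.** The expected skewness of Lp(a) explains the log transform and the robust regression. It does not explain a different assumption about what happens when a child stops drug. Apo B shows the contrast best, because it belongs to the same specialty panel and is drawn at the same visits. If a child stops after the week 12 dose and has no week 24 sample, Apo B is drawn around that child's baseline, while Lp(a) is predicted from the values at weeks 4, 8 and 12, all taken on drug.

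The trial has a single arm, so no control group undergoes the same imputation and offsets its effect. The SAP also plans no alternative imputation for Lp(a) that would show whether the choice matters.

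**Working it through.** The documents calculate no figure on this point, so there is none to reproduce.

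**1. When do the rules differ?** Dosing days come from the Part B schedule of events. The week 24 efficacy window is days 155 to 196, with target day 169 (SAP 10.2, Table 3).

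- Last dose at week 20: day 141 + 35 = day 176. Day 169 is still on treatment, so a missing value is MAR under both rules.
- Last dose at week 16: day 113 + 35 = day 148, before the window opens on day 155. The PMM would draw around baseline; Appendix 10.5 would not.
- Last dose at week 12: day 85 + 35 = day 120. Earlier last doses end sooner still.

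On the planned schedule the rules therefore differ only for a child whose last dose precedes week 20 **and** who has no week 24 Lp(a).

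**2. What would Appendix 10.5 impute from?** Part B schedules Lp(a) at baseline and weeks 4, 8, 12 and 24 only. For a child dosed through week 8 (day 57), the on-treatment period runs to day 57 + 35 = 92, so the week 12 value (day 85) is on treatment. All scheduled values before week 24 are then on-drug values. Off-drug information comes mainly from other discontinuers' observed week 24 values, or from later visits of a child who stopped after the baseline or week 4 dose.

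**3. Size on a simple mean.** Let k be the number of such children, N the Part B sample size and d the on-drug percent change in Lp(a). Assume that off-drug Lp(a) returns to baseline and that the MAR imputations average d. Then

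gap = (k/N) × |d|.

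N = 14 is from Protocol 11.2; SAP 2.2, written to Amendment 1, still gives 18. The documents give no d, so the range is an assumption.

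| k, N | d = −10% | d = −20% | d = −30% |
|---|---|---|---|
| 1, 14 | 0.7 | 1.4 | 2.1 |
| 2, 14 | 1.4 | 2.9 | 4.3 |
| 1, 18 | 0.6 | 1.1 | 1.7 |

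(Points. For example, 1/14 × 10 = 0.71 and 2/14 × 30 = 4.29.)

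**4. Check with robust regression.** The planned estimator is M-estimation, not a simple mean, so a small simulation was run. Its settings are assumptions: N = 14, log-normal Lp(a), dropout after week 12, off-drug truth at baseline, MAR regression imputation on the log scale, Tukey biweight M-estimation, 5 imputations and 120 replicates. The return-to-baseline draws were centred on log baseline. Mean estimates:

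| Effect set; children | Complete data | MAR | Return to baseline | MAR minus return |
|---|---|---|---|---|
| −20%; 1 missing | −16.65 | −18.04 | −16.76 | −1.28 |
| −20%; 2 missing | −16.33 | −19.32 | −16.77 | −2.55 |
| −20%; 1 missing, 1 observed off drug | −16.13 | −17.12 | −16.24 | −0.88 |
| 0%; 2 missing | 0.47 | 0.63 | 0.67 | −0.04 |
| +10%; 2 missing | 10.71 | 13.08 | 11.20 | +1.88 |

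The gaps of 1.28 and 2.55 are somewhat below the 1.4 and 2.9 of the formula. An observed off-drug value pulls the MAR imputations part of the way back.

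**5. Centring on the log scale.** A normal draw with variance v centred on log baseline has its median at baseline. Its mean percent change after back-transformation is exp(v/2) − 1. For an assumed log SD of 0.3 this is exp(0.045) − 1 = 4.6%; for 0.5 it is exp(0.125) − 1 = 13.3%. Centring on log baseline minus v/2 makes the mean percent change zero.

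**The case against.** A reader might infer that Lp(a) after discontinuation is handled as if every child were still on drug, and hence that the Lp(a) result is biased in the drug's favour. The documents do not support that.

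- Only absent values are imputed. Observed off-drug Lp(a) is used as observed and also enters the Appendix 10.5 model, whereas the PMM model excludes it.
- The trigger is narrow, and the protocol works against it. Section 8.4.2 encourages children who stop to attend all remaining visits, and section 9.1.2 asks for every effort to obtain the week 24 assessments.
- Direction is not established. The protocol's account of the adult and adolescent trial reports reductions in LDL-C, Apo B, non-HDL-C and total cholesterol, and gives no Lp(a) result.
- The estimand remains treatment policy. MAR appears under the ITT label elsewhere, in the MMRM of SAP 5.7.1.1.
- SAP 5.7.3 plans observed-data Lp(a) summaries with patient counts, and no formal test depends on the endpoint.

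These points make the size and direction conditional and limit the importance of the issue. They do not remove the inconsistency. The MMRM is a declared sensitivity analysis beside a PMM, whereas for Lp(a) MAR is the only imputed analysis. The observed-data summaries leave out the very children concerned. Nothing in the SAP suggests a deliberate exemption: Appendix 10.5 is introduced as covering the secondary endpoints in general, and it names triglycerides as an efficacy variable although SAP 4.8.2 lists them in the non-efficacy panel.

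**Conclusion.** The point holds as an unexplained inconsistency: the SAP states what it believes about children who stop drug, applies that belief to all other efficacy lipids and the responder endpoint, and drops it for Lp(a) under the same estimand.

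Overstatement of benefit follows only if three things are true together: at least one child stops before the week 20 dose and lacks a week 24 Lp(a); the drug lowers Lp(a); and Lp(a) returns towards baseline off drug. The sizes in the tables rest on those conditions and on assumed effects, since the documents give neither an Lp(a) effect nor a dropout rate. This is a modest matter on one secondary endpoint, but worth settling before the dropout pattern is known.

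**What to change.** In SAP 5.7.2.2, 5.7.3 and 10.5, give Lp(a) the two-pattern rule:

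- **Gaps within 35 days of the last dose:** MAR on the log scale, with a model fitted to on-treatment values only.
- **Later gaps:** draws on the log scale, with variance v equal to the conditional variance given log baseline, obtained as in Appendix 10.6, and centred on log baseline minus v/2, so that the back-transformed mean equals the child's own baseline.
- **Analysis:** keep the robust regression, and retain the present Appendix 10.5 imputation as a sensitivity analysis.
- **Cross-reference:** in SAP 5.7.3, replace the pointer to 5.7.2.1 for Lp(a) with 5.7.2.2.

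The cost is a few lines of SAP text and code, in a document that already needs updating from 18 to 14 patients. The drawbacks are a slightly smaller reported Lp(a) lowering if such a dropout occurs, and a v estimated from at most 14 children.
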